2.3 Benefit/Risk Assessment

Patients with recurrent HL will be enrolled in this study. The study intervention will be used/applied in accordance with the Prescribing Information for Sitavig [6].

Version 5.0

Page: 22 of 68

During the study, patients will be closely monitored for evidence of adverse events. Weighing between the potential risks of antiviral medication associated with the study and given the ability to mitigate risks through close monitoring, this study is considered clinically and ethically acceptable.

Relevant emerging safety data, e.g., serious adverse events (SAEs), suspected unexpected serious adverse reactions (SUSARs), and serious safety-related protocol deviations, will be communicated as soon as possible between the sponsor, all study sites and investigators and trial subjects according to the requirements of the FDA guideline on strategies to identify risks for clinical trials.

More detailed information about the known and expected benefits and risks and reasonably expected adverse events of 50 mg acyclovir buccal tablets may be found in the Prescribing Information for Sitavig [6].

The potential impact of COVID-19 on study participants will be evaluated before the start of enrollment and monitored during the study in accordance with FDA guidance [7].

Version 5.0 Page: 23 of 68

3. Objectives and Endpoints

| Objectives | Endpoints |
|---|---|
| To compare duration of episode (DOE) of cold sores when treated with Sitavig or placebo in participants experiencing a recurrence of herpes labialis (HL). | Duration of episode (DOE) will be measured in hours (using the Science 37 Platform), of a single treated HL lesion. Observation period to determine healing will last up to 14 days (DurEp14). Duration of episode (DOE) is defined as the time from the initiation of treatment (study intervention) initiation to the healing of primary lesions (loss of crust) for participants who experience a vesicular lesion. For participants whose primary lesions are not vesicular in nature, duration of episode is the time from study intervention initiation to the return to normal skin or to the cessation of symptoms, whichever comes last as determined by the independent blinded reader of the participant's face images using a 6-point Likert scale. |
| Secondary | using a 0-point Likert scale. |
| To compare the incidence of aborted lesions between participants receiving either Sitavig or placebo after experiencing prodromal symptoms of a recurrence of HL. To compare the incidence of recurrence of primary HL lesions between participants receiving either Sitavig or placebo during a 12-month follow-up period To compare the time to recurrence of primary HL lesions between participants receiving either Sitavig or placebo during a 12-month follow-up period. To assess safety and tolerability of the investigational products. | Incidence of aborted lesions, defined as treated HL lesions that do not progress to the vesicular or crust stage. A lesion that returns to normal skin without forming a vesicle or crust will be counted as an aborted lesion. Observation period to determine healing will last up to 14 days (Abort14). Incidence of recurrence of HL lesions during the 12-month follow-up period (IncRec12). Time to recurrence of HL lesions, measured in days from resolution of the cold sore treated in the Treatment phase until appearance of a cold sore during the follow-up period (TimeRec12). Safety and tolerability measured by the Incidence of Treatment-Emergent Adverse Events The percentage of participants who have at least one recurrence during the 12-month follow up period will be calculated. The time to first recurrence is determined by assessment from the investigator and documented using NRS symptom scores and face images using the Science 37 |

ersion 5.0 Page: 24 of 68

| | Objectives | | Endpoints |
|------|---|---|---|
| Othe | r | | |
| | To compare the duration of episode in participants who used Sitavig or placebo who initiated study intervention within 1 hour of prodromal symptoms and participants who initiated study intervention after 1 hour of prodromal symptoms. | • | Duration of episode (DOE) will be measured in hours (using the Science 37 Platform), of a single treated HL lesion in participants who initiation study intervention within 1 hour of onset of prodromal symptoms and participants who initiated study intervention more than 1 hour after onset of prodromal symptoms. |
| | To compare the time to cessation of symptoms in patients experiencing a recurrence of HL in participants who used Sitavig and placebo. | • | Time to cessation of symptoms, measured in hours from initial application of assigned study intervention. Cessation of symptoms is defined as the |
| • | To compare the quality of life in participants who used Sitavig and placebo. | | absence of sensations of pain, tenderness tingling, itching or discomfort at the site of the cold sore as measured by NRS. Observation period to |
| | To compare the 0-10 NRS HL symptoms by time point in participants who used Sitavig and placebo. | | determine healing will last up to 14 days (CesSymp14). |
| • | To evaluate the Global assessment at Day 14. | • | Quality of life score, as measured by the OHIP-14 questionnaire at 3, 7 and 14 days post-dose. |
| | To evaluate the incidence of detachment or swallowing within 6 hours of dosing, and | • | Global assessment of study intervention at Day 14. |
| | the incidence of replacing the tablet. | • | The change from baseline to post-dose in NRS. |
| | | • | The incidence of detachment or swallowing within 6 hours of dosing and the number (percentage) of subjects with the incidence. |
| | | • | The percentage of subjects who replace the tablet among those with detachment or swallowing within 6 hours of dosing. |

Version 5.0 Page: 25 of 68

4. Study Design

4.1 Overall Design

This is a randomized, multi-center, participant-initiated, double-blinded, single treatment study comparing acyclovir 50 mg muco-adhesive buccal tablet (Sitavig) to matching placebo (i.e., study intervention) in the treatment of Herpes Labialis (HL) in immunocompetent adults.

The study consists of a Screening Phase, Run-in Phase, Treatment Phase, Evaluation Phase and a Follow-Up Phase.

A visual presentation of the overall study design is provided in .

4.1.1 Study Design Phases

4.1.1.1 Screening/Randomization Phase

Participants will be screened for eligibility up to 35 days prior to study according to the inclusion/exclusion criteria. Participants will be assigned a screening number (SNR) and basic health information will be collected, and the participant will be assessed by the study investigator/designee. Eligible participants will be randomized into one of two study interventions. Participants will enter the Run-in Phase, which starts a six-month treatment eligibility window.

4.1.1.2 Run-in Phase

The Run-in Phase provides the opportunity for participants the time to spontaneously start a HL outbreak that would require treatment. Participants will be in contact with Science 37 using weekly virtual check-ins within the Science 37 Platform. Adverse events and concomitant medications could be recorded. Participants who do not develop an HL episode within six months will be withdrawn from the study.

4.1.1.3 Treatment Phase

Once participants experience prodromal symptoms, they will take face images and self-initiate treatment (study intervention) preferably **within one hour** and before the visible appearance of any signs of HL lesions according to the product instructions. Participants will also be completing HL symptom scores (pain, tenderness, itching, tingling and discomfort) as well as Quality of Life (QoL) scoring using the Oral Health Impact Profile (OHIP) and during the next 10 days within the Science 37 Platform. Participants will then be under evaluation for healing of the primary lesion(s) up to 14 days.

Participants will be asked to meet with the clinic via the Science 37 Platform within 36 hours of the start of study intervention (Day 1) and complete face images, symptom and QoL scores using the Science 37 Platform. Additionally, participants will complete face images, symptom and QoL scores on Days 2 through 13 with a virtual visit on Day 14 (+2 days), Visit 3 using the Science 37 Platform.

Version 5.0 Page: 26 of 68

4.1.1.4 Follow-up Phase

Participants will automatically transition to the Follow-up Phase after the completion of the Treatment Phase. Participants will be in contact with the Science 37 using weekly virtual check-ins within the Science 37 Platform with the purpose reporting any adverse events, concomitant medications or new outbreaks of HL. Potential new HL occurrences will be reviewed by the investigator using face images and symptom scores.

The duration of each patient's participation will be up to 20 months. For an overview on the trial design and trial procedures see Section 1.2.

4.3 Justification for Dose

Participants who self-initiate study intervention are instructed to apply one (1) 50 mg buccal tablet from the blister package to their upper gum area consistent with the Prescribing Information for Sitavig [6]. The second tablet/dose in the blister is provided as a backup in the event the first buccal tablet cannot be applied as instructed. See Section 6.5 related to applying a second buccal tablet.

4.4 End of Treatment Phase and End of Study Definitions

The end of the Treatment Phase is study is defined as the date of the last visit in the Treatment Phase (Visit 3) of the last participant in the study. The end of the study is defined as the date of the last follow-up visit (either by documented HL outbreak or at 12 months) of the last participant in the study.

A participant is considered to have completed the study if he/she has completed all phases of the study up to Follow up Phase as shown in the Schedule of Activities (Section 1.3).

5. Study Population

Prospective approval of protocol deviations to recruitment and enrollment criteria, also known as protocol waivers or exemptions are not permitted.

Version 5.0 Page: 27 of 68

5.1 Inclusion Criteria

Participants are eligible to be included in the study only if all of the following criteria apply:

Age

1. Males or females, 18 years of age or older inclusive;

Type of Participant and Disease Characteristics

- 2. History of recurrent HL lesions where:
 - a. Recurrence is defined as at least 4 episodes in the preceding 12 months;
 - b. At least half of the episodes should be vesicular in nature;
 - c. At least half of the episodes should be preceded by prodromal symptoms;
 - d. Herpes labialis lesions are characterized by their localization on the cutaneous and/or mucosal surfaces of the lips;
- 3. Willing to avoid, during the treatment phase, the use of anti-inflammatory (not including low-dose (81 mg) aspirin), anti-herpetic, antibiotic and antiviral agents as well as steroids or other natural products that would interfere with the immune system response;
- 4. Female participants of childbearing potential must be using a medically acceptable form of birth control during screening [e.g., hormonal contraceptives (oral, patch, injectable or vaginal ring), implantable device (implantable rod or intrauterine device), or a double barrier], abstinence or in same sex relationship and have a negative pregnancy test at Screening and prior to study drug administration. Female participants of non-childbearing potential must be amenorrheic for at least two years or have undergone surgical sterilization (i.e. tubal ligation/occlusion, hysterectomy and/or bilateral oophorectomy);
- 5. Agreement to abstain from any mechanical disruption of the prodromal area or lesion (i.e. scrubbing, lancing, shaving the area, rubbing with alcohol, application of heat emitting devices used for cold sore treatment, etc.);

Informed Consent and Other

- 6. Capable of giving signed informed consent as described in Section 10.1.4 which includes compliance with the requirements and restrictions listed in the informed consent form (ICF) and in this protocol;
- 7. Ability to understand and follow study-related instructions;
- 8. Be willing and able to participate in all scheduled visits, treatment plan, and trial procedures according to the clinical protocol.

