8.1.4 Treatment/Evaluation Phase (Day 1)

Participants who start to experience prodromal symptoms before the visible appearance of any signs of HL must document the start time of symptoms in Science 37 Platform, complete a pre-dose (immediately before dosing) 0-10 NRS cold sore symptom evaluation (pain, burning sensation, itching and swelling) and a face image. Prior to the start of study intervention, all WOCBP participants MUST perform a urine pregnancy test, and verify that the results are negative (not pregnant), and record in the Science 37 Platform. After verification of a negative pregnancy test result, the participant may self-initiate study intervention.

Any participant who has a positive pregnancy test or is not sure of the results must contact the Science 37 study team immediately. Participants with a verified positive pregnancy test must not self-administer study intervention and will be withdrawn from the study.

Participants must always record pre-dose NRS and a face image irrespective of the start time of prodromal symptoms in the Science 37 Platform. After the completion of all pre-dose procedures, participants will be instructed to self-administer one (1) tablet. Should the buccal tablet adhere to the upper gum correctly, a second dose/tablet is NOT applied. A second tablet in the treatment kit is provided and labeled "BACKUP". The backup tablet should only be used if an issue occurs applying the first tablet (see Section 6.5).

After dosing, participants will complete the 0-10 NRS cold sore symptom evaluation, and face images at 09:00, 14:00 and 19:00 that day within Science 37 Platform. Depending on time of day study intervention is started, some Day 1 assessments and face images may not be collected if the time (minus the 60 minute window) occurs before the time of dosing. If dosing is started after 19:00, then post-dose NRS and face images will be collected starting the next day at 09:00. All post-dose time point assessments (NRS and face images) have an allowable window of ± 60 minutes.

Version 5.0

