10.4 Appendix 4: Contraceptive Guidance and Collection of Pregnancy Information

Definitions:

Woman of Childbearing Potential (WOCBP)

A woman is considered fertile following menarche and until becoming post-menopausal unless permanently sterile (see below).

If fertility is unclear (e.g., amenorrhea in adolescents or athletes) and a menstrual cycle cannot be confirmed before first dose of study intervention, additional evaluation should be considered.

Women in the following categories are not considered WOCBP

- 1. Premenarchal
- 2. Premenopausal female with 1 of the following:
 - Documented hysterectomy
 - Documented bilateral salpingectomy
 - Documented bilateral oophorectomy

For individuals with permanent infertility due to an alternate medical cause other than the above, (e.g., mullerian agenesis, androgen insensitivity), investigator discretion should be applied to determining study entry.

Note: Documentation can come from the site personnel's: review of the participant's medical records or medical history interview.

Version 5.0 Page: 65 of 68

3. Postmenopausal female

- A postmenopausal state is defined as no menses for 24 months without an alternative medical cause.
- Females on hormone replacement therapy (HRT) and whose menopausal status is in doubt will be required to use one of the non-estrogen hormonal highly effective contraception methods if they wish to continue their HRT during the study. Otherwise, they must discontinue HRT to allow confirmation of postmenopausal status before study enrollment.

Contraception Guidance:

Female participants who become pregnant

- The investigator will collect pregnancy information on any female participant who becomes pregnant during the Treatment phase. The initial information will be recorded on the appropriate form and submitted to the sponsor within 24 hours of learning of a participant's pregnancy.
- The participant will be followed to determine the outcome of the pregnancy. The investigator will collect follow-up information on the participant and the neonate and the information will be forwarded to the sponsor. Generally, follow-up will not be required for longer than 6 to 8 weeks beyond the estimated delivery date. Any termination of pregnancy will be reported, regardless of fetal status (presence or absence of anomalies) or indication for the procedure.
 - While pregnancy itself is not considered to be an AE or SAE, any pregnancy

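### For a premenopausal woman with tubal ligation, inclusion 4 and Appendix 10.4 of the protocol give different answers on whether she must be pregnancy-tested before dosing

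*Protocol*

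**What the plan says.** Protocol section 5.1, inclusion 4, splits women into two groups. Those of non-childbearing potential have been without menses for at least two years or "have undergone surgical sterilization (i.e. tubal ligation/occlusion, hysterectomy and/or bilateral oophorectomy". For the others, "Female participants of childbearing potential must be using a medically acceptable form of birth control during screening", and they also need a negative pregnancy test at Screening and another before dosing.

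Appendix 10.4 sets its own default: "A woman is considered fertile following menarche and until becoming post-menopausal unless permanently sterile (see below". It then gives its exceptions under the line "Women in the following categories are not considered WOCBP". For premenopausal women the surgical exceptions are documented hysterectomy, "Documented bilateral salpingectomy" and documented bilateral oophorectomy. Tubal ligation or occlusion does not appear. For permanent infertility from another medical cause, the appendix says "investigator discretion should be applied to determining study entry".

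The status is then used in three places:

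- Section 8.1.4: "Prior to the start of study intervention, all WOCBP participants MUST perform a urine pregnancy test".
- Section 8.3.2 limits testing at Screening and on Day 1 to women of childbearing potential.
- Section 8.1.1 makes the Screening test, and the two home kits, conditional on being applicable.

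**The concern.** Two passages of the current Version 5.0 text define the same status differently, and a mandatory safety step depends on it. A site that classifies by inclusion 4 would not test a premenopausal woman with tubal ligation and might send her no kit. A site that classifies by Appendix 10.4 would test her at Screening and again before dosing.

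The timing makes this more than a matter of tidiness. Treatment is started by the participant at home, up to six months into the Run-in phase, after a Screening phase of up to 35 days. Even where a Screening test is done it can be months old at dosing, so the home test is the only scheduled pregnancy test close to exposure. Section 8.1.4 bars dosing after a verified positive result. Eligibility and the pregnancy kits are next reviewed at Visit 2, within 36 hours after the start of treatment. A test that was never required or supplied would come to light only after the tablet had been applied.

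**Working it through.** No formula applies. The check sets the two definitions side by side for each group of women and then follows the status to the procedures that use it.

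| Woman | Inclusion 4 (section 5.1) | Appendix 10.4 | Same answer? |
|---|---|---|---|
| Premenopausal, hysterectomy | Non-childbearing, named | Not WOCBP, named | Yes |
| Premenopausal, bilateral oophorectomy | Non-childbearing, named | Not WOCBP, named | Yes |
| No menses for two years | Non-childbearing (at least two years) | Not WOCBP (24 months; 2 × 12 = 24) | Yes |
| Premenopausal, tubal ligation/occlusion | Non-childbearing, named | WOCBP, by the default rule and because it is not listed | No |
| Premenopausal, bilateral salpingectomy | Not named; could be read into surgical sterilization | Not WOCBP, named | Unclear |

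The conflict is confined to premenopausal women. A postmenopausal woman who has had a ligation is non-childbearing under both texts.

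For the premenopausal woman with ligation, the consequences are:

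1. **Screening test** (inclusion 4, 8.1.1, 8.3.2): not required if inclusion 4 governs; required if Appendix 10.4 governs.
2. **Pre-dose test** (inclusion 4, 8.1.4, 8.3.2): the same split. Section 8.1.4 uses the term WOCBP, which is the term Appendix 10.4 defines; inclusion 4 does not use it.
3. **Home kits** (8.1.1): supplied only where applicable, so supply follows the same split.
4. **Contraception** (inclusion 4): not required if inclusion 4's own classification is used. If she is WOCBP the requirement applies in principle, but the methods are introduced as examples, so the text does not say whether the ligation would itself satisfy it.

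For bilateral salpingectomy, a strict reading of inclusion 4 would put the woman with those of childbearing potential, while the appendix takes her out. The result of the strict reading is at most an additional test or a stricter reading at entry.

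Both definitions stand in the body of Version 5.0. The difference does not come from the amendment log, a redaction or a broken table.

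**The case against.** Four arguments can be made against the point.

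- **The appendix is not exhaustive.** It never mentions ligation, and its discretion clause leaves room for other cases. It is true that WOCBP status is reached by default and omission, and the point should be put that way. But the clause concerns infertility from another medical cause, its examples are mullerian agenesis and androgen insensitivity, and it governs study entry. It does not clearly cover an elective procedure, and it says nothing about testing.
- **Inclusion 4 governs eligibility.** This has force for entry: inclusion 4 names ligation outright, and no section in the supplied text sends the reader to Appendix 10.4 for eligibility. It does not settle which definition controls the WOCBP test in section 8.1.4.
- **Other safeguards exist.** Exclusion 15 bars women who are pregnant or planning pregnancy, Screening collects menstrual information, and section 8.4.5 ends participation if pregnancy is supposed. Footnote a of the Schedule of Activities requires a negative pre-dose test without naming WOCBP. These reduce the risk but do not replace the test. The footnote has to be read with sections 8.1.4 and 8.3.2, since taken literally it would apply to every participant.
- **Salpingectomy may be no conflict at all.** Removal of both tubes can reasonably be read as surgical sterilization. That is why it is only a lesser mismatch here.

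A reader might go further and infer that, under Appendix 10.4, a woman with ligation is ineligible unless she uses a second contraceptive method. The documents do not support this: the methods in inclusion 4 are illustrative, and abstinence or a same-sex relationship is also accepted.

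**Conclusion.** The contradiction is real and narrow. For a premenopausal woman with tubal ligation or occlusion, the protocol gives two answers on the Screening test, the pre-dose test and the supply of kits. The answer on contraception is uncertain rather than contradictory, and bilateral salpingectomy is a lesser mismatch.

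The conclusion rests on reading Appendix 10.4 as it is written: fertile by default, with listed exceptions. It needs no assumption about numbers. The documents do not say how many participants are affected and give no basis for an estimate, so none is offered.

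A reader might also infer that inconsistent classification would feed through to the Per Protocol set, which is the primary efficacy population. The documents do not show this. Only major violations remove a subject (protocol section 9.3, SAP section 6.1), and nothing says a difference over childbearing status would be graded as major. The point concerns a safety procedure and leaves the sample size and the primary analysis method untouched. It is still worth correcting, because the step it leaves open is mandatory before dosing and cannot be put right afterwards.

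**What to change.** Reconcile inclusion 4 and Appendix 10.4 into a single definition of childbearing potential, kept in one place. It should assign tubal ligation/occlusion and bilateral salpingectomy explicitly to one side or the other. Inclusion 4 and sections 8.1.1, 8.1.4 and 8.3.2 should then refer to that definition and use one term for the status. The same edit can state whether the contraception requirement applies to each group. The classification itself is for the sponsor's medical lead; this review takes no position on it.

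The cost is wording in one criterion and one appendix, plus cross-references. Depending on the classification chosen, a few participants may need home test kits they would not otherwise have been sent.
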